8.1.2. Secondary Efficacy Assessments

The following secondary efficacy measures will be assessed at 40 weeks based on data collected at the times shown in the Study Schedule (see Section 1.3).

- Mean change in body weight
- Proportion of participants with HbA1c <7% (53 mmol/mol), ≤6.5% (48 mmol/mol), or <5.7% (39 mmol/mol)
- Mean change in fasting serum glucose values measured in the central laboratory
- Mean change in daily average 7-point SMBG profiles
- Proportion of participants who achieved weight loss ≥5%, ≥10%, and ≥15%
- Proportion of participants with HbA1c <7.0%, without weight gain (<0.1 kg) and without hypoglycemia (blood glucose <3.0 mmol/L [54 mg/dL] or severe hypoglycemia)
- Proportion of participants with HbA1c ≤6.5%, without weight gain (<0.1 kg) and without hypoglycemia (blood glucose <3.0 mmol/L [54 mg/dL] or severe hypoglycemia)
- Proportion of participants with HbA1c <7.0%, without weight gain (<0.1 kg) and without hypoglycemia (blood glucose <3.9 mmol/L [70 mg/dL])
- Proportion of participants with HbA1c ≤6.5%, without weight gain (<0.1 kg) and without hypoglycemia (blood glucose <3.9 mmol/L [70 mg/dL])

- Percentage change in daily mean insulin glargine dose

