8.3.4. Adverse Events of Special Interest

8.3.4.1. Hypoglycemia

Participants will collect information on episodes of hypoglycemia starting from Visit 2 until the last study visit (Follow-up Visit or Early Termination Visit). For that purpose, participants will be trained about signs and symptoms of hypoglycemia, how to treat hypoglycemia, and how to collect appropriate information for each episode of hypoglycemia in the study according to the SoA (Section 1.3). Site personnel will enter this information into the eCRF at each visit.

Investigators should use the following classification of hypoglycemia (ADA 2022c):

Level 1 hypoglycemia:

Glucose <3.9 mmol/L (<70 mg/dL) and ≥ 3.0 mmol/L (≥ 54 mg/dL): Level 1 hypoglycemia can alert a person to take action such as treatment with fast-acting carbohydrates. Providers should continue to counsel participants to treat hypoglycemia at this glucose alert value.

Level 2 hypoglycemia:

Glucose <3.0 mmol/L (<54 mg/dL): Level 2 hypoglycemia is also referred to as documented or blood glucose confirmed hypoglycemia with glucose <3.0 mmol/L (<54 mg/dL). This glucose threshold is clinically relevant regardless of the presence or absence of symptoms of hypoglycemia.

Level 3 hypoglycemia:

Severe hypoglycemia (in adults): A severe event characterized by altered mental and/or physical status requiring assistance for treatment of hypoglycemia. For example, participants had altered mental status, and could not assist in their own care, or were semiconscious or unconscious, or experienced coma with or without seizures, and the assistance of another person was needed to actively administer carbohydrate, glucagon, or other resuscitative actions. Glucose measurements may not be available during such an event, but neurological recovery attributable to the restoration of glucose concentration to normal is considered sufficient evidence that the event was induced by a low glucose concentration.

- The determination of a hypoglycemic event as an episode of severe hypoglycemia, as defined above, is made by the investigator based on the medical need of the participant to have required assistance and is not predicated on the report of a participant simply having received assistance.
- If a hypoglycemic event meets the criteria of severe hypoglycemia, the investigator must record the event as serious on the AE CRF and report it to Lilly as an SAE.

Nocturnal hypoglycemia:

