Efficacy 
 • To compare QW tirzepatide 5 mg 10 mg and/or 15 mg versus placebo when added to titrated basal insulin glargine alone or in combination with metformin with or without SGLT-2i, at 40 weeks for: 	
 • Proportion of participants with HbA1c <5.7% (39 mmol/mol) • Mean change in daily average 7-point self-monitored blood glucose profiles from baseline • Proportion of participants who achieved weight loss of $\geq 5\%$, $\geq 10\%$, and $\geq 15\%$ from baseline • Percentage change from baseline in daily mean insulin glargine dose • Proportion of participants with HbA1c <7.0%, without weight gain (<0.1 kg) and without hypoglycemia (blood glucose <3.0 mmol/L [54 mg/dL] or severe hypoglycemia) • Proportion of participants with HbA1c $\leq 6.5\%$, without weight gain (<0.1 kg) and without hypoglycemia (blood glucose <3.0 mmol/L [54 mg/dL] or severe hypoglycemia) • Proportion of participants with HbA1c <7.0%, without weight gain (<0.1 kg) and without hypoglycemia (blood glucose <3.9 mmol/L [70 mg/dL]) • Proportion of participants with HbA1c $\leq 6.5\%$, without weight gain (<0.1 kg) and without hypoglycemia (blood glucose <3.9 mmol/L [70 mg/dL]) • Proportion of participants with HbA1c <5.7%, without weight gain (<0.1 kg) and without hypoglycemia (blood glucose <3.0 mmol/L [54 mg/dL]) • Proportion of participants with HbA1c <5.7%, without weight gain (<0.1 kg) and without hypoglycemia (blood glucose <3.9 mmol/L [70 mg/dL])

Objectives	Endpoints/Estimands
Safety 
 To compare QW tirzepatide 5 mg, 10 mg, and 15 mg to placebo to the end of safety follow up for: 	
 TEAEs Early discontinuation of study drug due to AEs Adjudicated pancreatitis Serum calcitonin Incidence of allergic and hypersensitivity reactions Mean change in systolic and diastolic blood pressure and pulse rate from baseline Hypoglycemic episodes Incidence of initiation of rescue therapy for severe, persistent hyperglycemia

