4.4.2. Additional Secondary Endpoints

Additional secondary endpoints specified below will use the efficacy estimand and will be summarized by treatment and nominal visit.

- Proportion of participants with HbA1c <5.7% (39 mmol/mol)

- Mean change in daily average 7-point self-monitored blood glucose profiles from baseline
- Proportion of participants who achieved weight loss of $\geq 5\%$, $\geq 10\%$, and $\geq 15\%$ from baseline
- Percentage change from baseline in daily mean insulin glargine dose
- Proportion of participants with HbA1c $< 7.0\%$, without weight gain (< 0.1 kg) and without hypoglycemia (blood glucose < 3.0 mmol/L [54 mg/dL] or severe hypoglycemia)
- Proportion of participants with HbA1c $\leq 6.5\%$, without weight gain (< 0.1 kg) and without hypoglycemia (blood glucose < 3.0 mmol/L [54 mg/dL] or severe hypoglycemia)
- Proportion of participants with HbA1c $< 7.0\%$, without weight gain (< 0.1 kg) and without hypoglycemia (blood glucose < 3.9 mmol/L [70 mg/dL])
- Proportion of participants with HbA1c $\leq 6.5\%$, without weight gain (< 0.1 kg) and without hypoglycemia (blood glucose < 3.9 mmol/L [70 mg/dL])
- Proportion of participants with HbA1c $< 5.7\%$, without weight gain (< 0.1 kg) and without hypoglycemia (blood glucose < 3.0 mmol/L [54 mg/dL])
- Proportion of participants with HbA1c $< 5.7\%$, without weight gain (< 0.1 kg) and without hypoglycemia (blood glucose < 3.9 mmol/L [70 mg/dL])

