4.5.1. Exploratory Analysis not Specified in the Protocol

Table GPIM.4.2. Non-protocol Specified Exploratory Efficacy Analyses Not Controlled for Type I Error

Objective	Relative to the Efficacy Measure	Analysis Conducted in a Manner Similar to Section	Additional Information
To compare QW tirzepatide 5 mg, 10 mg, and 15 mg to placebo at 40 weeks for:	Change in self-monitored blood glucose profiles 
 • Morning premeal (fasting) • Morning 2-hour postmeal • Midday premeal • Midday 2-hour postmeal • Evening premeal • Evening 2-hour postmeal • Bedtime • Morning premeal to 2-hour postmeal excursion • Midday premeal to 2-hour postmeal excursion • Evening premeal to 2-hour postmeal excursion • the mean of all meals 2-hour excursion • the mean of all 7 point measurements • the mean of all pre-meal measurements • the mean of all 2-hour postprandial measurements 	MMRM model in Section 4.4.2.1	Use corresponding baseline parameter as a covariate.
	
 • Change in eGFR from baseline 	MMRM model in Section 4.4.2.1	Use baseline eGFR as a covariate.
	
 • Percentage of participants who achieved the following composite endpoints where No-Hypo is defined as BG <54 mg/dL (<3.0 mmol/L) and/or severe hypoglycemia: 
 ◦ HbA1c <5.7% & Weight Loss \geq5% & No-Hypo ◦ HbA1c <5.7% & Weight Loss \geq10% & No-Hypo 	Longitudinal logistic model in Section 4.4.2.2	None

Objective	Relative to the Efficacy Measure	Analysis Conducted in a Manner Similar to Section	Additional Information
	
 ○ HbA1c <5.7% & Weight Loss ≥15% & No-Hypo ○ HbA1c <5.7% & Weight Gain <0.1kg & No-Hypo ○ HbA1c ≤6.5% & Weight Loss ≥5% & No-Hypo ○ HbA1c ≤6.5% & Weight Loss ≥10% & No-Hypo ○ HbA1c ≤6.5% & Weight Loss ≥15% & No-Hypo ○ HbA1c <7.0% & Weight Loss ≥5% & No-Hypo ○ HbA1c <7.0% & Weight Loss ≥10% & No-Hypo ○ HbA1c <7.0% & Weight Loss ≥15% & No-Hypo 		

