4.6.3. Special Safety Topics

4.6.3.1. Hypoglycemic Events

Definitions of different categories of hypoglycemic events are mentioned below-

Level 1

Glucose <70 mg/dL (<3.9 mmol/L) and ≥ 54 mg/dL (≥ 3.0 mmol/L)

Level 1 hypoglycemia can alert a person to take action such as treatment with fast-acting carbohydrates. Providers should continue to counsel participants to treat hypoglycemia at this glucose alert value.

Level 2

Glucose <54 mg/dL (<3.0 mmol/L)

Level 2 hypoglycemia is also referred to as documented or blood glucose-confirmed hypoglycemia with glucose <54 mg/dL (<3.0 mmol/L). This glucose threshold is clinically relevant regardless of the presence or absence of symptoms of hypoglycemia.

Level 3 Severe

A severe hypoglycemic event is characterized by altered mental or physical status requiring assistance of another person to actively administer carbohydrate, glucagon, or other resuscitative actions for the treatment of hypoglycemia.

The determination of an episode of severe hypoglycemia is made by the investigator based on the medical need of the participant to have required assistance and is not predicated on the report of a participant simply having received assistance.

Examples of severe hypoglycemia in adults are-

- altered mental status and the inability to assist in their own care
- semiconscious or unconscious, or
- coma with or without seizures.

Nocturnal hypoglycemia: Nocturnal hypoglycemia is a hypoglycemia event, including severe hypoglycemia, which **occurs at night** and presumably during sleep.

To avoid duplicate reporting, all consecutive blood glucose values <70 mg/dL (3.9 mmol/L) occurring within a 1-hour period may be considered to be a single hypoglycemic event and the one with the lowest blood glucose value can be selected to be the representative. If two records with the same lowest values within an hour, the earlier occurrence will be selected.

A listing of level 2 and level 3 hypoglycemic events will be provided. Statistical summaries and analyses will exclude hypoglycemic events occurring after initiation of a new antihyperglycemic therapy. For severe hypoglycemia, level 1 and level 2 hypoglycemia, incidence as well as rate per patient year of exposure will be provided by treatment at specified time intervals. If data warrants, additional statistical analyses will be conducted on hypoglycemic incidence and rate.

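### Four of the six additional secondary composite responder endpoints let an unmeasured severe hypoglycemia count as success, and one of the four is defined in two ways

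*SAP*

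**What the plan says.** SAP Section 1.1 lists six composites among the additional secondary efficacy endpoints, and Section 4.4.2 repeats them. Each requires an HbA1c target, weight gain below 0.1 kg and absence of hypoglycemia. The hypoglycemia component is not the same in all six:

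- Two composites name severe events, for example "HbA1c <7.0%, without weight gain (<0.1 kg) and without hypoglycemia (blood glucose <3.0 mmol/L [54 mg/dL] or severe hypoglycemia". The other has the HbA1c target ≤6.5%.
- The HbA1c <5.7% composite at the same glucose limit does not: "HbA1c <5.7%, without weight gain (<0.1 kg) and without hypoglycemia (blood glucose <3.0 mmol/L [54 mg/dL" is followed only by closing brackets.
- All three composites at the higher limit also stop at glucose: "and without hypoglycemia (blood glucose < 3.9 mmol/L [70 mg/dL". For HbA1c <7.0% and ≤6.5% this wording comes from the protocol (Sections 3 and 8.1.2), for example "HbA1c <7.0%, without weight gain (<0.1 kg) and without hypoglycemia (blood glucose <3.9 mmol/L [70 mg/dL".

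Severe hypoglycemia is defined without a glucose value. SAP Section 4.6.3.1 says: "A severe hypoglycemic event is characterized by altered mental or physical status requiring assistance of another person". Protocol Section 8.3.4.1 adds: "Glucose measurements may not be available during such an event".

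SAP Table GPIM.4.2 (Section 4.5.1) lists ten further composites, "where No-Hypo is defined as BG <54 mg/dL (<3.0 mmol/L) and/or severe hypoglycemia". One of them has an HbA1c target of <5.7% and weight gain below 0.1 kg.

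**The concern.** An endpoint labelled as reaching target without hypoglycemia should not count someone who needed another person's help for a severe hypoglycemia. A glucose-only definition catches a Level 3 event only if a reading below the limit was taken, and the protocol says there may be none. SAP Section 4.4.2.2, which describes the analysis of these endpoints, has no rule that brings severe events in. The programmer must therefore either score such a participant as a success or make an undocumented decision.

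Two consequences follow. The 3.9 mmol/L version, meant to be the stricter one, can be passed by someone who fails the 3.0 mmol/L version at the same HbA1c target. And the HbA1c <5.7%, 3.0 mmol/L composite can give two different responder counts in one study report.

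**Working it through.** This is a question of definitions, so the check sets the texts side by side. The plan states no figure on this point to reproduce.

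**Step 1. Classify the six composites** (SAP Sections 1.1 and 4.4.2; Protocol Sections 3 and 8.1.2; SAP Table GPIM.4.2).

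| HbA1c target | Glucose limit (mmol/L) | Severe event is a failure? | Protocol endpoint? | Also in Table GPIM.4.2? |
|---|---|---|---|---|
| <7.0% | <3.0 | Yes | Yes | No |
| ≤6.5% | <3.0 | Yes | Yes | No |
| <7.0% | <3.9 | No | Yes | No |
| ≤6.5% | <3.9 | No | Yes | No |
| <5.7% | <3.0 | No | No | Yes, with severe events as failure |
| <5.7% | <3.9 | No | No | No |

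Glucose-only: 6 − 2 = 4. Of these, 2 are protocol endpoints and 4 − 2 = 2 are in the SAP only.

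**Step 2. Compare with the rest of the SAP.** At the 3.0 mmol/L limit there are 3 entries in Section 4.4.2 and 10 in Table GPIM.4.2, so 13 in all. Severe events count in 2 + 10 = 12 of them. The one exception is HbA1c <5.7% in Sections 1.1 and 4.4.2, and that is the entry duplicated in the table under the other rule.

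**Step 3. Conditions for misclassification.** All four must hold:

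- (a) the participant has a Level 3 event;
- (b) there is no reading below the limit at that event;
- (c) there is no other counted reading below the limit;
- (d) the HbA1c and weight criteria are met.

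**Step 4. Follow one such participant.** Suppose there is no counted reading below 3.9 mmol/L and week-40 HbA1c is below 5.7%.

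- HbA1c <7.0% and ≤6.5% at <3.0: failure, because the severe event counts.
- HbA1c <7.0% and ≤6.5% at <3.9: success.
- HbA1c <5.7% at <3.9: success.
- HbA1c <5.7% at <3.0: success under Section 4.4.2, failure under Table GPIM.4.2.

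If all composites used glucose alone, anyone with a reading below 3.0 would also have one below 3.9, so passing the 3.9 version would imply passing the 3.0 version. Adding severe events to the 3.0 version only breaks that ordering for HbA1c <7.0% and ≤6.5%.

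**Step 5. Size.** Protocol Section 1.1 plans 64 randomized participants per arm. If k participants in an arm are affected, its responder rate shifts by k/64:

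- k = 1: 1/64 = 1.56 percentage points
- k = 2: 2/64 = 3.13 percentage points

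The documents give no Level 3 rate, so k = 0 to 2 is an assumption. Counting severe events can only lower an arm's responder count. How the treatment difference moves depends on the arm in which the events fall.

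**The case against.** The strongest counter-argument is that the gap is almost empty. Participants on titrated insulin are encouraged to measure fasting glucose daily and to take 4-point profiles at least weekly (Protocol Section 6.1.3). Having a Level 3 event with no counted reading below 3.9 mmol/L would be unusual. Recent severe hypoglycemia or hypoglycemia unawareness is an exclusion (Protocol Section 5.2, criterion 14). The assumed range for the effect includes zero, and if nobody meets all four conditions the two definitions give identical counts. This stands. It makes the point weakest for the three composites at 3.9 mmol/L.

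It is also fair to say that severe events are not hidden. They are reported as SAEs, Level 2 and 3 events are listed, and SAP Section 4.6.3.1 plans incidence and rate of severe hypoglycemia by treatment, with a listing when events are few. But none of that corrects a responder count.

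Two of the four composites reproduce the protocol faithfully, so changing them departs from the protocol text. That is a cost, and a reason to document the change, but not a reason to keep a definition that contradicts the endpoint's label. SAP Section 4.1 allows such a change if it is justified in the SAP or the study report.

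Finally, the No-Hypo wording in Table GPIM.4.2 literally describes the presence of events. The intent is obvious and the point is editorial.

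**Conclusion.** The concern holds as a matter of wording. Four of the six composites can score a severe hypoglycemia as success, and one of the four has conflicting definitions within the SAP. The second defect exists in the text whatever the event rate.

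The practical effect is expected to be small: 1.6 percentage points per affected participant in an arm of 64, and 0 to 3.1 points if 0 to 2 participants per arm are affected. That range rests on an assumption, not on data in the documents. No direction of bias is established. These endpoints are outside type 1 error control, so the primary and key secondary conclusions do not depend on them. The correction should still be made, because the plan as written can misreport a named secondary endpoint and correcting it costs little.

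**What to change.** - Define the hypoglycemia component of all six composites as glucose below the stated threshold or severe (Level 3) hypoglycemia, in SAP Sections 1.1 and 4.4.2.
- Use the same definition in Table GPIM.4.2, and word No-Hypo there as the absence of these events. List the HbA1c <5.7%, weight gain <0.1 kg, 3.0 mmol/L composite once.
- Record the change and its reason in SAP Section 4.10, which now reads NA. Two of the affected composites are protocol endpoints. The two HbA1c <5.7% composites are not among the protocol's four, and the same entry can note that they were added.
- Make the change before unblinding, and align the protocol wording if the protocol is next amended.

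The cost is a wording change in three places and one log entry. For two composites it is a documented departure from the protocol text until the protocol is amended. Responder counts may be slightly lower. No new data are needed, because for any severe event "the investigator must record the event as serious on the AE CRF and report it to Lilly as an SAE" already applies (Protocol Section 8.3.4.1).

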1.2. Study Design

Study GPIM is a multicenter, randomized, double-blind, parallel, placebo-controlled Phase 3 study which will assess the efficacy and safety of the addition of 5 mg, 10 mg, or 15 mg tirzepatide, as compared with placebo in participants with T2DM as an add-on to titrated basal insulin alone or in combination with metformin with or without SGLT-2i over a 40-week treatment. The primary endpoint will be the mean change in HbA1c from baseline to 40 weeks.

This study includes an approximate 3-week screening/lead in period, a 40-week treatment period, and a 4-week safety follow-up (Figure GPIM.1.1).

Abbreviations: Met = metformin; QW = once-weekly; SGLT-2i = sodium-glucose transport protein 2 inhibitor.

^a Stabilization Period = first 4 weeks after randomization, with restricted insulin dose adjustments.

Basal insulin Titration Period = Weeks 4 to 40 (end of treatment), with unrestricted insulin dose adjustments.

Maintenance Period = Weeks 24 to 40 (end of treatment), the period when basal insulin dose is expected to be stable.

Figure GPIM.1.1. Illustration of study design for clinical protocol I8F-MC-GPIM.

Study Period I (Screening and Lead-in)*Screening (Visit 1)*

The purpose of screening procedures at Visit 1 is to establish initial eligibility and to obtain blood samples for laboratory assessments needed to confirm eligibility at Visit 2. Participants who meet all applicable inclusion criteria and none of the applicable exclusion criteria at Visit 1 will continue their pre-study therapy doses between Visits 1 and 2.

Lead-in (Visit 2 to Visit 3)

At Visit 2, the screening laboratory results will be reviewed. For those participants meeting all other eligibility requirements, a dilated fundoscopic examination performed by an ophthalmologist or optometrist, must be completed between Visit 2 and Visit 3 to ensure that participants with proliferative diabetic retinopathy, diabetic macular edema, or nonproliferative diabetic retinopathy who require acute treatment, are identified and not enrolled, unless there is a contraindication to dilate the eye (ie. closed angle glaucoma).

Study Period II (40-Week Treatment Period)*Randomization (Visit 3)*

At Visit 3, eligible participants will perform all required baseline study procedures (including the collection of all baseline laboratory measures and ECG) prior to randomization and prior to taking the first dose of study drug.

Treatment period: General Considerations

The treatment period will last 40 weeks, starting with a 4-week stabilization period immediately after randomization and followed by a 36-week insulin glargine titration period. The maintenance period is defined as a part of the titration period when insulin glargine dose is expected to be stable and optimized (Weeks 24 to 40 [Visits 17 to 19]).

The starting dose of tirzepatide will be 2.5 mg QW for 4 weeks, followed by an increase to 5 mg QW, for the duration of the study in the 5 mg group. For the 10 mg group, the starting dose of tirzepatide will be 2.5 mg QW for 4 weeks, then the dose will be increased by 2.5 mg every 4 weeks (2.5 to 5 to 7.5 to 10 mg) until the 10 mg dose is reached and maintained for the duration of the study. For the 15 mg group, the starting dose of tirzepatide will be 2.5 mg QW for 4 weeks, then the dose will be increased by 2.5 mg every 4 weeks (2.5 to 5 to 7.5 to 10 to 12.5 to 15 mg) until the 15 mg dose is reached and maintained for the duration of the study. For the placebo group, patients will inject matched QW placebo for the duration of the study.

*Post randomization period (end of Visit 3 to Visit 19):***Stabilization Period (End of Visit 3 through Visit 7 [Weeks 0 through 4])**

The main purposes of this period are to introduce randomized study drugs (QW tirzepatide or QW placebo) in a safe manner, to assure regular and correct use of the self-monitoring and insulin dose adjustment procedures, and to assure study diaries are completed correctly. Participants will be encouraged to perform 4-point SMBG profiles twice weekly (generally 3 days apart) during this period. Participants will be required to perform insulin dose assessment per the TTT algorithm twice weekly during this period. In an effort to allow appropriate time for

tirzepatide to reach steady state, insulin glargine dose adjustments during the 4-week stabilization period should be restricted to those needed in the case of significant safety risks due to inadequate insulin dose (hypoglycemia or severe hyperglycemia) in which case patients should be instructed to contact the sites to adjust the insulin glargine dose per the treat-to-target (TTT) algorithm. In addition, for participants with baseline HbA1c $\leq 8.0\%$, the insulin glargine dose will be decreased by 20% immediately after randomization, not later than 7 days after the first dose of study drug and will then remain unchanged during the stabilization period to decrease the risk of hypoglycemia. The insulin glargine dose will remain unchanged if baseline HbA1c is $>8.0\%$.

Titration Period (End of Visit 7 through Visit 19 [Weeks 5 through 40])

At the beginning of the titration period, the participant will be instructed to start using the TTT algorithm without restrictions in order to reach the optimal dose of insulin glargine as soon as possible. The participant will be requested to perform insulin dose assessment once weekly during this period.

Visit 99

Visit 99 is only applicable to participants who discontinue the study treatment prematurely before Week 40 and decline to complete the remaining study visits but are willing to return for Visit 99 at Week 40 after randomization. This visit is critical to ensure complete data collection for the primary and key secondary endpoints.

Study Period III (Safety Follow-up Period)

Safety follow-up (Visit 801) visits:

All participants who complete the treatment period are required to complete Visit 801, a safety follow-up visit, approximately 4 weeks after their last visit. Participants discontinuing the study early and performing an early termination (ET) visit will also be asked to perform the safety follow-up visit, so that the safety follow-up visit will be their final visit. During the safety follow-up period, participants will not receive study drug. Initiation of new antihyperglycemic therapy for the safety follow-up period will not be classified as “rescue therapy.”

2. Statistical Hypotheses

The alternative hypotheses for the primary objective are the following:

- $H_{15,1}$: QW tirzepatide 15 mg is superior to placebo when added to titrated basal insulin glargine alone or in combination with metformin with or without SGLT-2i for mean change in HbA1c from baseline at 40 weeks.

and/or

- $H_{10,1}$: QW tirzepatide 10 mg is superior to placebo when added to titrated basal insulin glargine alone or in combination with metformin with or without SGLT-2i for mean change in HbA1c from baseline at 40 weeks.

The above two hypotheses will be tested in parallel, each at a 2-sided significance level of 0.025.

The alternative hypotheses for the key secondary objective controlling for type 1 error rate are the following:

- $H_{5,1}$: QW tirzepatide 5 mg is superior to placebo when added to titrated basal insulin glargine alone or in combination with metformin with or without SGLT-2i for mean change in HbA1c from baseline at 40 weeks.
- $H_{15,2}$: QW tirzepatide 15 mg is superior to placebo when added to titrated basal insulin glargine alone or in combination with metformin with or without SGLT-2i for mean change in body weight from baseline at 40 weeks.
- $H_{10,2}$: QW tirzepatide 10 mg is superior to placebo when added to titrated basal insulin glargine alone or in combination with metformin with or without SGLT-2i for mean change in body weight from baseline at 40 weeks.
- $H_{5,2}$: QW tirzepatide 5 mg is superior to placebo when added to titrated basal insulin glargine alone or in combination with metformin with or without SGLT-2i for mean change in body weight from baseline at 40 weeks.
- $H_{15,3}$: QW tirzepatide 15 mg is superior to placebo when added to titrated basal insulin glargine alone or in combination with metformin with or without SGLT-2i for the proportion of participants with $HbA1c < 7\%$ (53 mmol/mol) at 40 weeks.
- $H_{10,3}$: QW tirzepatide 10 mg is superior to placebo when added to titrated basal insulin glargine alone or in combination with metformin with or without SGLT-2i for the proportion of participants with $HbA1c < 7\%$ (53 mmol/mol) at 40 weeks.
- $H_{5,3}$: QW tirzepatide 5 mg is superior to placebo when added to titrated basal insulin glargine alone or in combination with metformin with or without SGLT-2i for the proportion of participants with $HbA1c < 7\%$ (53 mmol/mol) at 40 weeks.
- $H_{15,4}$: QW tirzepatide 15 mg is superior to placebo when added to titrated basal insulin glargine alone or in combination with metformin with or without SGLT-2i for the proportion of participants with $HbA1c \leq 6.5\%$ (48 mmol/mol) at 40 weeks.
- $H_{10,4}$: QW tirzepatide 10 mg is superior to placebo when added to titrated basal insulin glargine alone or in combination with metformin with or without SGLT-2i for the proportion of participants with $HbA1c \leq 6.5\%$ (48 mmol/mol) at 40 weeks.

- $H_{5,4}$: QW tirzepatide 5 mg is superior to placebo when added to titrated basal insulin glargine alone or in combination with metformin with or without SGLT-2i for the proportion of participants with $HbA1c \leq 6.5\%$ (48 mmol/mol) at 40 weeks.
- $H_{15,5}$: QW tirzepatide 15 mg is superior to placebo when added to titrated basal insulin glargine alone or in combination with metformin with or without SGLT-2i for mean change in fasting serum glucose (FSG) from baseline at 40 weeks.
- $H_{10,5}$: QW tirzepatide 10 mg is superior to placebo when added to titrated basal insulin glargine alone or in combination with metformin with or without SGLT-2i for mean change in FSG from baseline at 40 weeks.
- $H_{5,5}$: QW tirzepatide 5 mg is superior to placebo when added to titrated basal insulin glargine alone or in combination with metformin with or without SGLT-2i for mean change in FSG from baseline at 40 weeks.
- $H_{15,6}$: QW tirzepatide 15 mg is superior to placebo when added to titrated basal insulin glargine alone or in combination with metformin with or without SGLT-2i for the proportion of participants with $HbA1c < 5.7\%$ (39 mmol/mol) at 40 weeks.
- $H_{10,6}$: QW tirzepatide 10 mg is superior to placebo when added to titrated basal insulin glargine alone or in combination with metformin with or without SGLT-2i for the proportion of participants with $HbA1c < 5.7\%$ (39 mmol/mol) at 40 weeks.

Operationally the hypotheses will be evaluated by 2-sided tests.

